Objectives	
Primary Objectives
 
 To determine the feasibility of imaging apoptotic activity in carotid atherosclerotic plaques of asymptomatic patients or patients that have been previously symptomatic with TIA only with significant carotid artery disease by using ^{99m}Tc-rhAnnexin V-128 and to report the prevalence of abnormal ^{99m}Tc-rhAnnexin V-128 scans. 
Secondary Objectives:
 
 To establish the uptake of ^{99m}Tc-rhAnnexin V-128 in a control group of participants with normal carotid ultrasounds. To assess the ^{99m}Tc-rhAnnexin V-128 uptake versus plaque(s) echogenicity and echolucency. To measure the aortic uptake of ^{99m}Tc-rhAnnexin V-128 and assess the correlation with its carotid uptake.
Rationale	Annexin V is an endogenous human protein that binds to phosphatidylserine (PS), a constitutive anionic phospholipid of the plasma membrane of all mammalian cells, that is only expressed only on the surface of physiologically stressed, depolarized, or apoptotic cells. Technetium-99m (^{99m}Tc) is a medical isotope widely used in diagnostic imaging. ^{99m}Tc -labeled annexin V has demonstrated the ability to image cellular stress, membrane depolarization (i.e. acute and chronic pain in animal models and cell culture), apoptosis and necrosis in a variety of inflammatory diseases including atherosclerosis, myocarditis, acute heart transplant rejection, rheumatoid arthritis, prosthetic joint infection and Crohn's disease in both animal models and humans.
Planned number of participants	Thirty five evaluable asymptomatic or previously symptomatic with TIA only patients with diagnosed carotid atherosclerotic plaque. In addition, a control group of 10 participants with normal carotid ultrasound imaging will be enrolled.

Study Protocol

	Fifteen patients and 5 normals will be recruited in the first part of the trial, as a Proof of Concept (PoC). The PoC study will assess the imaging potential of ^{99m}Tc -rhAnnexin V-128 in terms of imaging quality, uptake and medical relevance to enable the decision to continue the clinical investigation with the remaining 20 patients.
Study design and Methodology	
This is a single-centre, single dose, PoC, Phase II study. Participants who have signed the informed consent and are eligible to participate in the study will undergo the following assessments:
 
 • A screening visit will be conducted within 8 weeks ^{99m}Tc-rhAnnexin V-128 imaging. Eligible and consenting participants will undergo a limited physical examination (height, weight, BMI), vital signs (systolic and diastolic blood pressure, heart rate), blood analysis and urinalysis. The following blood analysis will be conducted: CBC with automated differential, general chemistry panel (SMA-20) including, PT/PTT, INR (international normalized ratio for PT values) and assessment of anti-annexin V-128 antibodies. • Carotid ultrasound will be carried out within 8 weeks prior to the ^{99m}Tc-rhAnnexin V-128 planar and SPECT/CT imaging. Imaging visit: planar and dedicated SPECT/CT imaging of the carotids and aorta will be done 60 minutes after injection of tracer, and 120 minutes after injection. Vital signs assessment/participant monitoring will be done throughout the visit. • Within 24 hours after the administration of ^{99m}Tc-rhAnnexin V-128, participants will be called for the assessment of possible adverse events. • 30 +/- 3 days post ^{99m}Tc-rhAnnexin V-128 injection, all participants will return to clinic for a final blood sampling to rule out the development of anti-annexin V-128 antibodies. The following blood analysis will also be conducted: CBC with automated differential, general chemistry panel (SMA-20) including, PT/PTT, and INR. • Once the first 15 patients and 5 normals have been administered with ^{99m}Tc-rhAnnexin V-128 and have performed the imaging visits, the Data Monitoring Committee will review the images. The visual assessment of the scans in these first 20 participants will support the continuation or the termination of the Phase II study.
Treatment	After reconstitution and radiolabeling, ^{99m}Tc -rhAnnexin V-128 is administered as a single intravenous bolus of 350 MBq +/- 10% at the imaging visit (Day 0).
Inclusion/exclusion criteria	
Inclusion criteria
 
For all participants:
 
 1. Males and females age 18 years or greater 2. Able and willing to comply with the study procedures 3. Negative pregnancy test for women of childbearing potential at screening and on the day of administration of ^{99m}Tc-rhAnnexin V-128.

Study Protocol

	
For participants with carotid artery disease:
 
 4. Evidence of 50% or more carotid stenosis in one or more carotid arteries on carotid ultrasound within 2 years; 
For control participants:
 
 4. No significant carotid artery disease on carotid ultrasound; 
Exclusion criteria
 
 1. Previous carotid stenting or endarterectomy or stroke; 2. Diagnosis of vasculitis, dissection, or non-atherosclerotic carotid disease (Ehlers-Danlos, Marfans); 3. Pregnancy or lactation; 4. History of any disease or relevant physical or psychiatric condition or abnormal physical finding which may interfere with the study objectives at the investigator judgment; 5. Know hypersensitivity to the investigational product or any of its components; 6. Claustrophobia or inability to lie still in a supine position; 7. Participation in another clinical trial within 4 weeks before study inclusion, except for patients who have participated or who are currently participating in a study without any study drug administration; 8. Unwillingness to provide consent.
Study duration and assessments	Maximum 3 months (+/- 3 days) including the screening period for an individual participant
Safety	
Venous blood samples will be drawn for each participant at screening and at 30 +/- 3 days post IP administration for laboratory analysis (CBC with diff., SMA-20, PT/PTT, INR).
 
To rule out development of anti-annexin V-128 antibodies, venous blood samples will also be drawn for each participant at screening and 30 +/- 3 days post ^{99m}Tc-rhAnnexin V-128 injection. Assays for anti-rhAnnexin V-128 IgG and IgM antibodies will be performed in serum samples by ELISA. For this purpose, 10 mL of blood will be collected for each assay.
 
24 hours post IP injection, each participant will be called to review any signs or symptoms of AEs. If any, adverse event(s) will be reported and recorded in the Electronic Case Report Form (e-CRF).
 
All participants will undergo a physical examination (height, weight, BMI) and vital signs (systolic and diastolic blood pressure, heart rate) at screening visit and before and after injection of the radiotracer.
 
Adverse events will be collected in the e-CRF.

Study Protocol

2

Statistics

A sample size of 30 patients produces a 96 to 98% confidence interval equal to the sample proportion plus or minus 0.17 to 0.20 when the estimated proportion is 0.3 to 0.5. Sample size was also estimated for the comparison of ^{99m}Tc-rh-Annexin-V 128 uptake in asymptomatic patients with carotid disease versus controls using a 5% significance level and power of 95%. Based on the results from the Phase I clinical trial in 12 healthy volunteers and by allowing attrition, we plan to recruit 10 participants in the control group and 35 patients with carotid plaque.

Among the 35 patients and 10 normals, 15 patients from the disease group and 5 normals from the control group will be enrolled in the PoC phase, which is believed to provide sufficient data to demonstrate the potential of ^{99m}Tc-rhAnnexin V-128 imaging in carotid atherosclerotic plaque.

Primary endpoint of PoC:

The feasibility of imaging apoptotic activity in carotid atherosclerotic plaques using ^{99m}Tc-rhAnnexin V-128 will be assessed by the data monitoring committee (visual image review and consensus). The frequency and severity of abnormal carotid scans will be determined in the patient and normal groups.

Primary endpoint of Phase II:

To determine the prevalence of abnormal ^{99m}Tc-rhAnnexin V-128 planar and SPECT/CT imaging.

Secondary endpoints:

Descriptive statistics of ^{99m}Tc-rhAnnexin V-128 uptake in control participants will be presented by areas of interest to assess the background uptake profile.

^{99m}Tc-rhAnnexin V-128 carotid uptake will be related to the ultrasound data of plaque echogenicity and echolucency.

^{99m}Tc-rhAnnexin V-128 uptake in carotids will be correlated to aortic uptake in all participants.

Safety:

Adverse events will be listed on an individual basis, including relationship, and severity, and will be summarized by System Organ Class (SOC) and Preferred Term (PT). Participants with more than one adverse event within a particular SOC and PT will be counted only once for that SOC and PT. The incidence of adverse events will also be summarized by severity.

All other safety variables will be tabulated at each measuring time. Hematology, clinical chemistry, urinalysis and immunogenicity data will be analysed with respect to the normal ranges of values provided by the laboratory. Similarly, descriptive statistics will also be provided for vital signs, physical examination, etc.

Table 1 – Visit Schedule

Study Procedures	Screening (Within 8 weeks prior to Day 0)	Planar and SPECT/CT Visit (Day 0)	24 hours post IP injection¹	30 ± 3 days post IP injection (Day 30)
Written informed consent	x			
Inclusion/exclusion criteria	x	x		
Medical history	x			
Concomitant medications	x	x	x	x
Physical examination (height, weight, BMI)	x	x		
Vital signs (BP, HR)	x	x		
Lab analysis (hematology, PT/PTT/INR, biochemistry, urine)	x			x
Immunogenicity by ELISA ²	x			x
Pregnancy test	x	x		
Carotid ultrasound ³	x			
rh-Annexin V-128 administration		x		
Planar & SPECT/CT imaging		x		
Adverse events assessment		x	x	x

¹ Within 24 hours after injection of ^{99m}Tc-rh-Annexin V-128, each participant will be called to review any signs or symptoms of AEs.

² Anti-rhAnnexin V-128 IgG and IgM antibodies will be quantified in serum samples by ELISA. For this purpose 10 mL blood samples will be collected at screening and Day 30 (±3 days) post administration of investigation product. Serum will be prepared, divided into six aliquots and frozen (-80°C). Three out of six serum samples per time-point will then be shipped to the [REDACTED] central laboratory.

³ Within 8 weeks prior to ^{99m}Tc-rh-Annexin V-128 imaging.

Study Protocol

□

2. List of abbreviations

AE	Adverse Event
BUN	Blood Urea Nitrogen
e-CRF	Electronic Case Report Form
CRO	Clinical Research Organization
CRP	C-Reactive Protein
CT	Computed Tomography
DMC	Data Monitoring Committee
ELISA	Enzyme-Linked Immuno-absorbent Assay
ESR	Erythrocyte Sedimentation Rate
FDA	Food and Drug Administration
FDG	18-fluorodeoxyglucose
GCP	Good Clinical Practice
Hb	Hemoglobin
HPLC	High-Performance Liquid Chromatography
IBD	Inflammatory Bowel Disease
ICF	Informed Consent Form
ICP-MS	Inductively Coupled Plasma Mass Spectrometry
ICP-OES	Inductively Coupled Plasma Optical Emission Spectrometry
ICRP	International Commission on Radiological Protection
IEC	Independent Ethics Committee
IL-6	Interleukine-6
IMP	Investigational Medicinal Product
INR	International Normalized Ratio
IRB	Institutional Review Board
ITLC	Instant Thin Layer Chromatography
MBq	Mega Becquerel
MIRD	Medical Internal Radiation Dose
MCV	Mean Corpuscular Volume
MedDRA	Medical Dictionary For Regulatory Activities
NOAEL	No Observed Adverse Effect Level

Study Protocol

PET	Positron Emission Tomography
PBS	Phosphate Buffered Saline
PoC	Proof of Concept
PS	Phosphatidylserine
PT	Prothrombin Time
PTT	Partial Thromboplastin Time
PV	Pharmaco Vigilance
QA	Quality Assurance
QC	Quality Control
RBC	Red Blood Cell
RCP	Radiochemical Purity
REB	Research Ethic Board
ROI	Region of Interest
RR	Respiratory Rate
████	████████████████████ (CRO)
SAE	Serious Adverse Event
SEC-HPLC	Size-Exclusion HPLC
SD	Standard Deviation
SOP	Standard Operating Procedure
SPECT	Single-Photon Emission Computed Tomography
TBR	Target to background ratio
TLC	Thin Layer Chromatography
US	Ultra Sounds
UV/Vis	Ultraviolet/Visible
WBC	White Blood Cell
WFI	Water For Injection
WHO	World Health Organization
VOI	Volumes Of Interest

□

3. Background and Rationale

Atherosclerosis is projected to become an internationally leading cause of mortality¹⁻³ and is the underlying pathophysiology responsible for angina, myocardial infarction, transient ischemic attacks and stroke. Atherosclerosis is an inflammatory disease process that begins with the formation of lipid-rich fatty streaks in vascular endothelium, and eventually resulting in complexly remodeled plaques⁴ consisting of a central lipid rich and necrotic core bound by a thin fibrous cap^{5, 6}. The fibrous cap is prone to eroding or rupturing leading to thrombus generation and resulting in severe ischemic injury of the tissue bed supplied by the thrombosed vessel^{7, 8}. Rupture-prone plaque is referred to as vulnerable plaque⁹.

Vascular inflammation can be imaged with 18-fluorodeoxyglucose positron emission tomography (FDG PET). FDG uptake imaged with PET is considered to be a marker of macrophage expression within plaque¹⁰. Macrophages are one of the main cellular components of inflamed atherosclerotic plaque¹¹. However, a major limitation of FDG PET is the normal diffuse uptake in non-vascular structures (myocardium and neck musculature) that leads to poor specificity with false positive results. This extravascular uptake represents a challenge for imaging vasculature, particularly the coronaries and carotids¹². Other cells adjacent to the target of interest and within the field of view may also take up FDG, resulting in difficulty with separating FDG uptake in inflamed lesions from surrounding tissues.

Immunohistochemical examination of ruptured vulnerable plaques has demonstrated that there is increased expression of apoptotic and disintegrated macrophages within the lipid rich necrotic core¹³⁻¹⁵. In addition to macrophages, smooth muscle cells undergoing apoptosis or programmed cell death have been localized within the fibrous components of plaque^{16, 17}. Further, expansion of the necrotic core may be related to plaque destabilization^{15, 18, 19}. Thus, imaging apoptosis may identify vulnerable plaque and be a more specific imaging approach for advanced and complicated plaque than FDG PET.

Apoptosis is an energy-dependent process of programmed cell death that ensues following the initiation of an internal and regulated suicide program²⁰. A hallmark feature of apoptosis is the externalisation of phosphatidylserine (PS) as the cell transitions towards shrinkage, degradation of DNA and eventual fragmentation²⁰. Annexin V is an endogenous human protein (molecular weight 36 kDalton) produced by epithelial cells. Annexin V binds with very high affinity to PS, and serves the purpose of labeling cells for phagocytosis²¹. Radiotracers that bind specifically to Annexin V have been developed for the non-invasive detection of apoptotic activity using imaging modalities such as SPECT. Early clinical cardiovascular studies with ^{99m}Tc labeled Annexin V and SPECT imaging demonstrated significant radiotracer uptake in 7 patients with acute myocardial infarction²² and in 4 patients with carotid artery atherosclerosis²³. Validation studies in experimental rabbit models of atherosclerosis correlated uptake of ^{99m}Tc labeled Annexin V with histological degree of apoptosis, atherosclerotic lesion severity and macrophage burden²⁴ and plaque vulnerability²⁵. Thus, ^{99m}Tc labeled Annexin V has potential for imaging atherosclerotic lesions and identifying advanced lesions with greater apoptosis and vulnerability.

^{99m}Tc-HYNIC-Annexin V was the early ^{99m}Tc labeled Annexin V used successfully in several

clinical studies but had a major limitation with very high renal uptake resulting in a high patient radiation dose and limiting abdominal imaging²⁶. A novel form of Annexin-V with an endogenous ^{99m}Tc chelating site (rhAnnexin V-128) has been developed²⁷. ^{99m}Tc labeled rhAnnexin V-128 has more rapid renal clearance than ^{99m}Tc-HYNIC-Annexin V and similar detection of apoptosis in animal models²⁷.

^{99m}Tc labeled rhAnnexin V-128 has been evaluated in a Phase I clinical trial at the University of Ottawa Heart Institute in 12 normal volunteers. No significant adverse effects were observed. Blood clearance was rapid. Greatest radiotracer uptake was in the kidneys, bladder (due to rapid kidney clearance), liver and lungs. Total effective dose (IRCP 60) for ^{99m}Tc labeled rhAnnexin V-128 was 7.7 + 0.8 uSv/MBq and was significantly less than 11.0 + 0.8 uSv/MBq reported for ^{99m}Tc-HYNIC-Annexin V-128²⁸.

Ultrasound imaging can provide further insight into the morphology of plaque. B-mode ultrasound derived measures of plaque echogenicity can predict the content of soft lipid tissue and the amount of calcification in carotid plaque^{29, 30}. Echogenic plaque is typically composed of fibrous tissue and calcification, while echolucent plaque is lipid-rich^{29, 30}. Plaque morphology by ultrasound has predictive value for identifying patients at increased risk of ischemic cerebrovascular events independent of degree of stenosis and vascular risk factors³¹. A recent review of ultrasound, computed tomography and magnetic resonance imaging of the carotid arteries concluded that ultrasound was preferable at the present time due to high spatial and temporal resolution, safety, low cost and wide availability³².

The goal of the present investigation is to assess the feasibility of ^{99m}Tc-rhAnnexin V-128 planar and SPECT imaging as a technique for detection of apoptotic carotid plaque in asymptomatic patients with significant carotid artery disease. This investigation will determine the prevalence of significant apoptotic activity in carotid plaque in patients with carotid disease. ^{99m}Tc-rhAnnexin V-128 uptake in the carotid arteries as a measure of apoptotic activity will be compared to plaque ultrasound-based echogenicity and echolucency, measures of plaque vulnerability. Aortic uptake of ^{99m}Tc-rhAnnexin V-128 will be imaged and related to carotid uptake of ^{99m}Tc-rhAnnexin V-128.

4. Study Objectives

The primary objective of this investigation is:

- To determine the feasibility of imaging apoptotic activity in carotid atherosclerotic plaques of asymptomatic or previous symptomatic with TIA only patients with significant carotid artery disease by using ^{99m}Tc-rhAnnexin V-128 imaging and to report the prevalence of abnormal ^{99m}Tc-rhAnnexin V-128 scans.

The secondary objectives are:

- To establish the uptake of ^{99m}Tc-rhAnnexin V-128 in a control group of participants with normal carotid ultrasounds.
- To assess the ^{99m}Tc-rhAnnexin V-128 uptake versus plaque echogenicity and echolucency.
- To measure aortic uptake of ^{99m}Tc-rhAnnexin V-128 and assess the correlation with its

carotid uptake.

5. Hypotheses

5.1 Primary Hypothesis

^{99m}Tc-rhAnnexin V-128 imaging can be used to detect apoptosis in carotid plaque in asymptomatic or previously symptomatic with TIA only patients with at least 50% carotid stenosis as defined by ultrasound. In this population, the anticipated prevalence of carotid apoptosis will be 0.3 to 0.5.

8.1 Inclusion criteria

For all participants:

1. Males and females age 18 years or greater;
2. Able and willing to comply with the study procedures;
3. Negative pregnancy test for women of childbearing potential at screening and on the day of administration of ^{99m}Tc-rhAnnexin V-128.

For participants with carotid artery disease:

4. Evidence of 50% or more carotid stenosis in one or more carotid arteries on carotid ultrasound within 10 years;

For control participants:

4. No significant carotid artery disease on carotid ultrasound;

8.2 Exclusion criteria

1. Previous carotid stenting or endarterectomy, or stroke;
2. Diagnosis of vasculitis, dissection, or non-atherosclerotic carotid disease (Ehlers-Danlos, Marfans);
3. Pregnancy or lactation;
4. History of any disease or relevant physical or psychiatric condition or abnormal physical finding which may interfere with the study objectives at the investigator judgment;
5. Known hypersensitivity to the investigational product or any of its components;
6. Claustrophobia or inability to lie still in a supine position;
7. Participation in another clinical trial within 4 weeks before study inclusion, except for patients who have participated or who are currently participating in a study without any study drug administration;
8. Unwillingness to provide consent.

8.3 Source of Study Population

The carotid artery study population will be adult male and female patients who are referred to the outpatient cardiology clinics and/or the non-invasive Diagnostic Imaging Department at the University of Ottawa Heart Institute. The control population will be healthy volunteers who do not have carotid atherosclerosis as assessed by ultrasound and whose lab values are within the normal range.

8.4 Participants Study Identification

Each participant will be identified with a participant ID number. A unique participant identification number (Participant ID) will be assigned at the start of the screening period to each participant who signs the informed consent form. This number will identify the participant throughout the study. Participant IDs will include the 2-digit protocol number (04), the 2-letter code (CA) and a 3-digit participant number (ex: 04-CA001 for first participant in).

8.5 Premature Discontinuation

The withdrawal of a study participant is mandatory in the following cases:

Study Protocol

- Pregnancy
- Protocol violation determined as critical
- Lost to follow-up
- Serious inter-current illness or other safety reasons for what the Investigator considers it is in the best interest of the participant to withdraw from the study
- Screening failure

A “screening failure” is a participant who has signed the informed consent, but who does not meet all selection criteria following the screening evaluations. For participants not considered eligible after the screening period, the reason for not being eligible must be documented. No additional assessments are needed. Participant information collected at the screening visit will be entered in the eCRF and will be used in the study analysis.

The participants may withdraw from the study if they decide to do so, at any time and irrespective of the reason, or this may be the Investigator’s decision. The primary reason for a participant’s withdrawal from the study should be determined if possible. The date and reason for discontinuation will be documented in the e-CRF.

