13.1 Definition of Adverse Events

An AE is defined as any untoward medical occurrence in a participant and which does not necessarily have a causal relationship with the investigational product. An AE can therefore be any unfavourable and unintended sign (including an abnormal laboratory finding), symptom, or disease, temporally associated with the use of an investigational product, whether or not causally related to the investigational product.

AEs will be reported, if applicable, from the signing of the informed consent until the last study-related procedure.

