6.1.3.1 Adverse events

All original AE/SAE terms will be coded using the Medical Dictionary for Regulatory Activities (MedDRA) Version 19.0.

Adverse events (AEs) will be listed on an individual basis, including relationship and severity, LLT (Lowest Level Term) and verbatim term. Treatment emergent Adverse events (TEAEs) and Adverse Drug Reactions (ADRs) will be summarized by System Organ Class (SOC) and Preferred Term (PT), grouping patients versus control subjects, and also including a total column for all subjects who received Annexin. Participants with more than one adverse event within a particular SOC and PT will be counted only once for that SOC and PT reporting the highest level in severity. The incidence of TEAEs and ADRs will also be summarized by subject type and severity.

Listings and summaries of serious adverse events (SAEs), adverse events leading to withdrawal and listings of deaths will also be presented.

Treatment Emergent Adverse Events and Adverse Drug Reactions will be defined as below:

Version: 01 Page: **27 of 167**

- Treatment Emergent Adverse Events: Events that emerge after the ^{99m}Tc-rhAnnexin V-128 injection and up to 30 days after the injection that were absent before it or worsen relative to the pre-treatment state.
- Adverse Drug Reactions: Treatment emergent adverse events possibly or probably related to study treatment.

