11 APPENDICES

11.1 Standard listings

All listings must contain examples of possible data and be presented in fixed font (arial) with a minimum size as 8.

Version: 01 Page: **43 of 167**

Listing 16.2.1.1: Subject Disposition – All Subjects

Subject ID	Screening date	Informed consent date	Subject group*	Visit 1 date	Phone call 2 date	Visit 3 date	Premature study discontinuation date	FAS	PP	Safety
PAT_PATNUMBER	PAT_FIRSTVISITDAT E	PAT_INFCONS_DATE	PAT_INFCONS_TYPE	PATV_VISITDATE	PATV_VISITDATE	PATV_VISITDATE	SD_DATE	[Derived data]	[Derived data]	[Derived data]
04-CA-001	11/03/2011	11/03/2011	Patient	11/04/2011	12/04/2011	11/05/2011		Yes	Yes	Yes
04-CA-002	09/04/2011	09/04/2011	Control	09/04/2011	10/04/2011	10/05/2011		Yes	Yes	Yes
04-CA-003	10/07/2011	10/07/2011	Control	15/07/2011	16/07/2011	NA	10/08/2011	Yes	No	Yes

Data Source Table: W_PATIENT, W_PATIENTVIS, W_SD.

Note: NA = Not Available for patient early withdrawal

^{*} Patient = Subject with asymptomatic plaque; Control = Healthy volunteer

Confidential

Version: 01 Page: **44 of 167**

Listing 16.2.1.2: Subject Disposition – Study Withdrawals

Subject ID	Screening date	Informed consent date	Informed consent type*	Premature study discontinuation date	Reason for withdrawal	Explanation	Notes	FAS	PP	Safety	
PAT_PATNUMBER	PAT_FIRSTVISITDATE	PAT_INFCONS_DATE	PAT_INFCONS_TYPE	SD_DATE	SD_OUTCOME	SD_OUTCOME_SP	SD_NOTES	[Derived data]	[Derived data]	[Derived data]	
04-CA-001	11/03/2011	11/03/2011	Patient	10/05/2012	XXXXXX	XXXXXX	XXXXXX	Yes	No	Yes	
04-CA-002	09/04/2011	09/04/2011	Control	10/05/2012	XXXXXX	XXXXXX	XXXXXX	Yes	No	Yes	
04-CA-003	10/07/2011	10/07/2011	Control	10/05/2012	XXXXXX	XXXXXX	XXXXXX	Yes	No	Yes	

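### Mandatory withdrawal is not split at the single injection, so an injected participant can lose the only scheduled post-dose laboratory and antibody sample with no dose saved

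*Protocol*

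**What the plan says.** Protocol 8.5 introduces five grounds with the words "The withdrawal of a study participant is mandatory in the following cases". They are pregnancy, a protocol violation judged critical, loss to follow-up, serious intercurrent illness or another safety reason that the Investigator thinks warrants withdrawal, and screening failure. Nothing in the list depends on whether the injection has been given. The section asks for the primary reason where it can be found, and adds: "The date and reason for discontinuation will be documented in the e-CRF". One sentence waives further work, "No additional assessments are needed", but it belongs to the paragraph on screening failures. SAP 4.3.3.6 carries the same text, in the part of the SAP that reproduces protocol information.

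Each participant receives one injection (Protocol 9.4, SAP 4.2.2). For antibodies, footnote 2 of the visit schedule (Protocol Table 1) says "10 mL blood samples will be collected at screening and Day 30". The same table places the only scheduled post-dose laboratory panel at Day 30. The synopsis and SAP 4.3.4 say that "all participants will return to clinic for a final blood sampling".

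On adverse events, Protocol 13.1 says "AEs will be reported, if applicable, from the signing of the informed consent until the last study-related procedure". SAP 6.1.3.1 counts as treatment-emergent those events that arise "up to 30 days after the injection that were absent before it" or that worsen relative to the pre-treatment state.

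**The concern.** In a repeated-dose trial, mandatory withdrawal protects the participant from further exposure. Here, once the Day 0 injection and scans are done, there is no exposure left to prevent. What remains is a telephone call and a Day 30 visit for concomitant medications, adverse events, laboratory tests and antibodies, with no imaging and no radiation. Withdrawing an injected participant therefore stops only safety follow-up, at the point where it is most wanted.

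The antibody sample matters most. The stated purpose of the Day 30 draw is to exclude an antibody response to the product, and no other post-dose antibody sample is scheduled. A participant who misses it contributes no scheduled immunogenicity result. Adverse event counts are affected too. A withdrawn participant stays in the safety set (SAP 5.2), and the adverse event tables take enrolled participants as the denominator (footnote to SAP Table 14.3.1.2), although collection of non-serious events may have stopped.

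**Working it through.** The plan states no figure on this point, so the check is mainly a comparison of texts, followed by a short illustration of size.

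**Which grounds matter after injection.** Screening failures occur before dosing. Participants lost to follow-up cannot be sampled under any rule. That leaves three of the five grounds: pregnancy, critical violation, and illness or safety. For critical violations, SAP 5.1.2 already removes major deviations from the per-protocol set, so ending safety follow-up adds no protection to the efficacy analysis.

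**What other provisions supply for an injected, withdrawn participant.**

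| Provision | Covers | Leaves open |
|---|---|---|
| Samples after any adverse event (Protocol 10.2, SAP 6.1.3.2) | Laboratory values near the event; the SAP also names immunogenicity, Protocol 10.2 does not | Needs an adverse event; an early sample is not a Day 30 antibody sample |
| Serious adverse event follow-up (Protocol 13.2) | The serious event itself | No Day 30 sample; non-serious events |
| Pregnancy reporting (Protocol 13.3) | The pregnancy and its outcome | No Day 30 sample |
| Statement that all participants return at Day 30 (synopsis, SAP 4.3.4) | The general schedule | Not reconciled with mandatory withdrawal |

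**Size.** The documents give no rate of withdrawal after injection, so the number of lost visits is assumed. Planned numbers are 35 patients and 10 controls (Protocol 12.1), 45 in all.

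- One lost Day 30 visit is 1/35 = 2.9% of patients, 1/10 = 10.0% of controls, or 1/45 = 2.2% overall.
- With zero cases among n sampled, the exact (Clopper-Pearson) two-sided 95% upper limit is 1 − 0.025^(1/n).

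| Group | Full n | Limit | n after loss | Limit |
|---|---|---|---|---|
| Patients | 35 | 10.0% | 34 | 10.3% |
| Controls | 10 | 30.8% | 9 | 33.6% |
| All | 45 | 7.9% | 44 | 8.0% |
| All, three lost | 45 | 7.9% | 42 | 8.4% |

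- Adverse event window in an assumed extreme case, with withdrawal just after the 24-hour call: 30 − 1 = about 29 days in which non-serious events may go uncollected for that participant.

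**The case against.** The strongest reply is that the protocol nowhere says withdrawal ends safety follow-up. The only waiver of assessments is confined to screening failures, the general schedule brings everyone back at Day 30, and adverse event reporting ends at the last study procedure, not at withdrawal. On that view this is silence to be clarified. It is right that no text forbids or waives the Day 30 assessment for an injected participant, and a reader who infers such a waiver goes beyond the documents. But section 8.5 is more than silent. It makes withdrawal from the study compulsory, and a site could reasonably take that to end attendance. The general schedule does not say which instruction prevails.

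The reply continues that the compulsion is weaker than it looks. The illness or safety ground turns on the Investigator's judgement, and a violation must be judged critical. Only pregnancy operates without such a judgement, and tests must be negative at screening and on Day 0. This stands, and it is one reason to expect few cases.

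A reader might also infer that results will go missing selectively in the participants with a safety finding. The documents support this only weakly. Such a participant will usually have an adverse event, which is itself counted and triggers laboratory sampling. For pregnancy or a violation without an adverse event, there is no evident reason why absence would be related to the antibody result. What remains is that an early sample may not show what the Day 30 antibody sample would.

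Finally, the shell of SAP Listing 16.2.1.1 carries the footnote "Note: NA = Not Available for patient early withdrawal", with an example control in the safety set whose third visit is missing. It is tempting to read this as a rule that withdrawn participants skip Day 30. It is mock data: the same example participant appears as not injected in Listing 16.2.5.1, and the footnote would equally fit voluntary withdrawal or loss to follow-up.

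**Conclusion.** The point holds in a limited form. Protocol 8.5 mandates withdrawal without regard to whether the single injection has been given. Read plainly, it can cost an injected participant the one scheduled post-dose laboratory and antibody sample, and later non-serious adverse events, with no dose avoided. The partial safeguards elsewhere do not supply the Day 30 antibody sample.

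The size is small. The number affected is unknown and probably low, the loss of precision is trivial under the assumed one to three lost visits, and the laboratory table shells report missing counts. Imaging is complete on Day 0 and membership of the full analysis set and safety set does not depend on Day 30, so the prevalence and uptake endpoints are untouched. Nor does this show that the safety conclusions would be biased. The verdict assumes that at least some sites or monitors would take withdrawal from the study in its ordinary sense. The consent form is not in the public documents and may address follow-up after withdrawal. This is a change worth considering, not one on which the trial's results depend.

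**What to change.** Amend Protocol 8.5 so that a participant who meets a withdrawal criterion after injection still completes the 24-hour call and the Day 30 adverse event, laboratory and antibody assessment, unless that person withdraws consent to follow-up. Add that a critical violation after injection does not end safety follow-up. Carry the same sentences into SAP 4.3.3.6, which only copies the protocol.

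No new visit, sample or table is needed. The cost is a short protocol amendment, with ethics board or regulatory approval or notification as Protocol 15.5 requires, and a few more attendances at visits already scheduled.
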